3.2.2 Comparison of the proportion of PTS-positive patients between ZNS post-op and Placebo

$$H_0: p_{ZNS_{post-op}} - p_{Placebo} = 0$$
 $H_A: p_{ZNS_{post-op}} < p_{Placebo}$

We hypothesize that ZNS post-op will reduce the proportion of PTS-positive patients by an absolute difference of 25% as compared to placebo. Our one-sided hypothesis is supported by animal studies, and lack of any evidence of hearing loss as a side effect of ZNS in human studies. The statistical testing will be performed using Bonferroni method to control for type I error rate at one-sided alpha level of 0.0125.

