Multiple imputation will be used to impute data in each of the study groups. A progressive penalty of $\delta_i = k_i \times \log{(OR)}$ will be added to imputed values in ZNS arm where (i) OR is the Odds ratio estimate for ZNS as compared to Placebo from the primary logistic regression analysis and (ii) $k_i = 1, 0.95, 0.90, \dots 0.05, 0, 1.05, 1.10,\dots$ thus k ranges from 1 (equivalent to MI approach based on MAR) to 0 (or higher), until the conclusion of the primary analysis is overturned (i.e., p<0.05 is lost at, this value of k_i being the 'tipping point'). Rubin's method will be used to combine the primary endpoint treatment effects across imputations for each value, k_i , of the penalty. Forest plots will be used to graphically display the penalty value that results in loss of statistical significance.

```
SAS code sample for Sensitivity analysis is provided below:

**Step 1: Generate 10 datasets by imputing the missing data**;

PROC MI DATA=X SEED=<value> NIMPUTE=10 OUT=MI_OUT1 NOPRINT;

CLASS GROUP;

VAR AGE PTA LSurg......;

FCS LOGISTIC (PTS);

RUN;

**Step 2: Generate 10 complete datasets from the 10 monotonized datasetsin Step 1 for missing values in the drug arm,
```

```
subtract DELTA derived above from their imputed data.**;
proc mi data=YYY NIMPUTE=1 SEED=<value> OUT=YYY shift;
by group;
class group;
var AGE PTA LSurg.....;
monotone method=logistic;
mnar adjust(PTS / shift=DELTA adjustobs=(group='1'));
**Step 3: Apply the primary MMRM to the 10 complete datasets in Step 2**;
proc genmod data=YYY shift descending;
by imputation;
class group;
model PTS = group AGE PTA LSurg......;
ods output GEEModPEst=gmparms;
**Step 4: Obtain the pooled inference from 10 sets of estimates from Step 3**;
PROC MIANALYZE PARMS=GMPARMS COVB=GMCOVB PARMINFO=GMPINFO WCOV BCOV
   TCOV:
   MODELEFFECTS group;
RUN:
```

7.1.2 Analysis for secondary outcome measures.

The focus of the study is to determine efficacy of ZNS for treatment of acute hearing loss based on the testing of hypothesis for primary outcome. In addition, we will also conduct analysis to evaluate other important audiologic measures. The secondary outcome measures are key audiological and clinical assessments of change in cochlear function and hearing loss: DPOAEs, ECochG, WIN testing. They will be measured as continuous level variables. We do not plan any adjustment of alpha error for multiple comparisons.

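### Sensitivity 2 (the tipping-point analysis) contradicts itself on the direction of the shift, places MAR at the wrong k, and judges tipping at p<0.05 instead of one-sided 0.0125

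*SAP*

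**What the plan says.** SAP 7.1.1, Sensitivity 2 (Protocol 12.2.1 carries the same text and code sample):

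- Base imputation: "Multiple imputation will be used to impute data in each of the study groups".
- Shift: a progressive penalty k × log(OR), with OR for ZNS relative to placebo, which "will be added to imputed values in ZNS arm".
- Values of k: 1, 0.95, 0.90 and so on down to 0, then 1.05, 1.10 and upward, with the gloss "thus k ranges from 1 (equivalent to MI approach based on MAR) to 0 (or higher".
- Stopping rule: continue "until the conclusion of the primary analysis is overturned". The criterion given beside it is "p<0.05 is lost at, this value of" k. No sidedness is stated.
- Code sample: the Step 2 comment says "subtract DELTA derived above from their imputed data". The statement below it has "shift=DELTA adjustobs=(group='1", with no minus sign, and runs by group. Step 1 is already an imputation of PTS, and Step 2 starts from its output. Step 3 refers to a primary MMRM. Step 4 pools the group effect.
- Label: the list of sensitivity analyses describes this one as resting on data missing at random.

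The primary conclusion is defined elsewhere. SAP 3.2.2 uses Bonferroni to "control for type I error rate at one-sided alpha level of 0.0125", and SAP 2.7 gives the same level for each ZNS-placebo comparison. On missing data, SAP 5.2 expects fewer than 5% of subjects to be lost, and SAP 2.7 expects few or none.

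**The concern.** A tipping-point analysis should make the missing ZNS outcomes progressively worse and report how bad they must be before the positive result is lost. Three features work against that here. The sign in the prose makes them better when ZNS looks effective. The stated MAR point does not match a shift that vanishes at k=0. The level at which the result counts as lost is looser than the level at which it was won.

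This is the plan's only search for how bad the missing ZNS outcomes must be to overturn the primary result. If the prose were programmed literally, it would report no tipping point for a near-threshold positive result that does have one. If the sign were put right but p<0.05 kept, it could still miss that point. The remaining choices would then fall to the programmer, possibly after results are known.

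**Working it through.** **Inputs.** From SAP 2.7: 78 per arm, PTS 50% on placebo and 25% on ZNS, one-sided alpha 0.0125, stated power 80.4%. From SAP 5.2: under 5% missing and 10 imputations. The counts in step 3 are assumed, because the documents give none.

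**1. Check of the design figure.** Exact enumeration of the one-sided Fisher test (78 v 78, 50% v 25%) gives power 80.7% at 0.0125, against the stated 80.4%. The same design has 88.0% at 0.025 and 93.0% at 0.05, so 0.05 is a clearly easier level.

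**2. Direction and anchor at the design rates.** OR = (0.25/0.75)/(0.50/0.50) = 0.333 and log(OR) = −1.0986. Imputed ZNS risk is expit(logit(0.25) ± k × log(OR)). At k=1 the odds of 0.333 become 0.333 × 0.333 = 0.111 if the shift is added (risk 10%), or 0.333/0.333 = 1 if it is subtracted (risk 50%). The last column starts from placebo risk and adds the shift.

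| k | Within-arm, added | Within-arm, subtracted | Placebo start, added |
|---|---|---|---|
| 0 | 25% | 25% | 50% |
| 0.5 | 16.1% | 36.6% | 36.6% |
| 1 | 10% | 50% | 25% |
| 2 | 3.6% | 75% | 10% |

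With within-arm imputation the shift is zero, and the analysis is MAR, at k=0. Only the placebo start makes k=1 roughly MAR.

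**3. Effect on the p-value.** Method: no covariates; arm risks drawn from Beta(r+0.5, n−r+0.5); a logit shift on imputed ZNS patients only; 78 per arm after imputation. Logistic: log OR pooled by Rubin's rules with variance W + 1.1B and a normal reference. Pooled Fisher: one-sided p converted to z, averaged and converted back, as SAP 5.2 describes; this ignores between-imputation variance. All p-values are one-sided, and logistic unless stated.

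Example (a): 3 missing per arm (3/78 = 3.8%), 22/75 v 37/75. Observed OR = (22 × 38)/(53 × 37) = 0.426. Observed-data Fisher p = 0.0095, which passes.

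| | k=0 | k=1 | k=2 | k=3 | limit |
|---|---|---|---|---|---|
| Added | 0.0066 | 0.0052 | 0.0045 | – | 0.0040 |
| Subtracted | 0.0066 | 0.0087 | 0.0111 | 0.0130 | 0.0153 |

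- Added never tips.
- Subtracted crosses 0.0125 at k about 2.7 (imputed ZNS risk about 80%), or about 1.5 by pooled Fisher.
- At the limit all 3 missing ZNS patients are PTS-positive. The p-value of 0.0153 is 0.031 two-sided, so p<0.05 is not lost on either sidedness.
- Placebo start: 0.0065 at k=1 and 0.0087 at k=0, where the downward run stops; then 0.0052 at k=2, back in favour of ZNS.

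Example (b): 4 missing per arm (4/78 = 5.1%, just over the ceiling), 22/74 v 37/74, Fisher 0.0092. Added falls from 0.0064 to 0.0032. Subtracted crosses 0.0125 at k about 1.9 (risk 69%), with limit 0.0192 (0.038 two-sided).

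Results that do not tip by either test: 19/74 and 20/74 v 37/74 (logistic limits 0.0052 and 0.0083; pooled Fisher 0.0069 and 0.0110).

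Results where the test decides: 21/75 v 37/75 has logistic limit 0.0100 (no tip) but tips at k=4.0 by pooled Fisher. 23/76 v 38/76, with 2 missing per arm, has logistic limit 0.0123 (no tip) but tips at k=1.7 by pooled Fisher.

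**4. How often it could matter.** I enumerated outcomes at the design rates with the penalty correctly signed and took those that pass Fisher. With 3 missing per arm, about 8% tip at some k by logistic; with 2 missing, about 2%; with 1, none. By k=1 with 3 missing, none tips by logistic and about 0.9% by pooled Fisher. None tips at one-sided 0.05.

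**5. Code steps.** If Step 1 fills PTS, no missing PTS is left for Step 2 to shift. An MNAR adjustment is not a missing-at-random analysis. The primary test is Fisher's exact test, and the plan contains no MMRM.

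**The case against.** A reader might infer that Sensitivity 2 simply cannot overturn a positive result. The documents do not support that as a flat statement. It follows only from the added reading. The word penalty and the subtract comment point the other way. The code is a sample with dotted variable lists; it never shows how DELTA is computed and does not state which PTS level the adjustment models, so the missing minus sign settles nothing. The direction is contradictory, not settled against ZNS. The p<0.05 criterion is a separate defect: it hides or delays tipping but does not cause the sign problem.

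The benign reading also deserves weight. If imputation starts from the placebo distribution, k=1 is about MAR, as labelled, and running k down to 0 is a real penalty. Imputing in each group could merely mean that every arm is imputed. But the by-group statement, the subtract comment and values of k above 1 all contradict this reading. It also ends at placebo risk, short of the 80% tipping point in example (a).

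The practical effect is small, and that objection stands. Tipping needs a near-threshold result, and often an imputed ZNS risk well above the placebo rate.

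A reader might also infer that Sensitivity 1 will be run as MAR, because its template repeats the SAP 5.2 block. Its prose clearly requires placebo-based imputation, and the code is only an elided template. Within-arm and placebo-based imputation give 0.0066 v 0.0087 in (a) and 0.0064 v 0.0093 in (b), the same conclusion. They part at 23/74 v 37/74 (0.0101 v 0.0140), where the observed-data Fisher test already fails at 0.0146. That is a minor gap.

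**Conclusion.** Sensitivity 2 is internally inconsistent and wrong as specified. The prose sign contradicts the stated purpose and the code comment, k=1 is not MAR under within-arm imputation, and the tipping level is not the level that defines the primary conclusion. The code steps, the missing-at-random label and the MMRM reference also need correcting. Read literally, the prose would show no tipping point in example (a), where a correctly signed penalty tips at k about 2.7 (logistic) or 1.5 (pooled Fisher). Keeping p<0.05 would miss the logistic tip even with the right sign.

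This should be fixed, but its reach is limited to near-threshold results, given under 5% expected missing data, and the primary test does not change. The sizes rest on assumed counts, equal missingness per arm and no covariates. The sign, anchor and alpha findings do not depend on those assumptions.

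**What to change.** In the prose, comment and code of SAP 7.1.1 and Protocol 12.2.1:

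- Define the shift as −k × log(OR) on the log-odds of being PTS-positive, with the event level stated, in each ZNS arm. Let k=0 be MAR, and raise k through 1 (about placebo risk) and beyond.
- Apply the shift in the step that imputes PTS; Step 1 must leave PTS missing.
- Declare tipping when one-sided p exceeds 0.0125, and name one test in advance: the pooled logistic group effect already used in Steps 3 and 4, or the pooled Fisher rule of SAP 5.2. The tipping k depends on this choice.
- Relabel the analysis as MNAR and delete the MMRM reference.
- If a placebo-based start was intended, say so, remove the each-group wording and k above 1, and run k from 1 through 0 to negative values. This traces essentially the same path (0.0065 and 0.0087, against 0.0066 and 0.0087, in example (a)).

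Minor: the Sensitivity 1 template should show the placebo-based imputation statement and the group effect that its prose already requires.

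The cost is wording and code templates, before database lock. No data are needed.

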#### Primary analysis.

Frequency and relative frequency will be used to describe the distribution of the primary outcome measure in each study group. To assess efficacy, Fisher's exact test will be used to compare the proportion of subjects with PTS positive in ZNS group with the proportion of patients with PTS positive in the placebo group.

To provide an estimate of treatment effect a supportive logistic regression analysis will be done with covariates: age, pre-op hearing dichotomized to normal to minimal hearing loss and slight to mild loss, noise exposure history dichotomized to high risk and low risk, exposure categorized as low (8-hour equivalent A-weighted sound level in decibel (LAeq8hr) < 80 dBA), moderate (LAeq8hr > 80 dBA but < 90 dBA), or high (LAeq8hr > 90 dBA).

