2.7 Sample Size Determination for The Primary Efficacy Outcome Measure

The primary efficacy outcome will be the proportion of PTS positive subjects defined as the ratio of PTS-positive subjects to total number of subjects in each study arm/group. Using pilot data from a retrospective chart review of 75 similar patients undergoing \geq 1-hour drill noise exposure, we estimate the proportion of PTS positive subjects in the placebo group will be 50%. We hypothesize that the expected effect of ZNS either pre-op or post-op will be a 50% reduction of the proportion of subjects with PTS positive as compared to placebo group. This is the desired clinically significant effect for treating hearing loss for single dose of 100 mg ZNS.

The sample size for this study was calculated for the planned comparisons of each of the ZNS groups with the placebo group using a balanced design and a one-sided alpha level of 0.0125 Based on the data from our retrospective study, using Fisher's exact test we estimated that 78 subjects in the ZNS group and 78 subjects in the placebo group will be needed to provide us with 80.4 % power to detect a 50% reduction in the proportion of PTS positive subjects *(from 50% to*

^{**}Dispensed on the day of surgery with instruction to take first dose prior to surgery and second dose after surgery.

^{***} Plasma sample for PGx will be collected at baseline visit. Plasma sample for ZNS level and PGx, electrolyte panel, BUN, Cr, ALT, and AST will be collected 12 hours after first dose.

25% corresponding to an absolute proportion difference of 25%) at the 1-sided alpha level of 0.0125 for each ZNS-Placebo group comparison. A total of 234 subjects will be enrolled to be randomized in this study. All efforts will be made minimize and eliminate drop outs. Given the short term-follow-up of study subjects in a period where they are under medical care, few, if any, drop-outs or lost to follow-up are expected.

Sample size calculations were carried out using PROC POWER procedure in SAS 9.4.

3 Study Outcomes

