 z_a = the $100(1-\alpha)^{th}$ percentile of the standard Normal distribution.

The proportion difference between groups is: $\mathbf{D} = \mathbf{p_1} - \mathbf{p_2}$

The lower (l_D) and the upper limits (u_D)of 100 (1- α)% confidence interval for D will be calculated as:

$$l_D = D - \sqrt{(p_1 - l_1)^2 + (u_2 - p_2)^2}$$

$$u_D = D + \sqrt{(p_2 - l_2)^2 + (u_1 - p_1)^2}$$

A supportive logistic regression analysis will be done with covariates: age, pre-op hearing dichotomized to normal to minimal hearing loss and slight to mild loss, noise exposure history dichotomized to high risk and low risk, exposure categorized as low (8-hour equivalent A-weighted sound level in decibel (LAeq8hr) < 80 dBA), moderate (LAeq8hr > 80 dBA but < 90 dBA), or high (LAeq8hr > 90 dBA).

```
PROC LOGISTIC DATA=X;
CLASS GROUP;
   MODEL PTS = COVARIATE1 COVARIATE2.. ;/*Covariates are as mentioned above*/
RUN;
```

Sensitivity analysis of the primary endpoint

The potential impact of missing primary endpoint data will be explored in sensitivity analyses using multiple imputation. Two sensitivity analyses performed:

Sensitivity 1: MI analysis under the missing not at random assumption (MNAR) Sensitivity 2: Logistic regression tipping point analysis under the assumption of data missing at random.

Sensitivity 1

Proc MI procedure in SAS will be used to impute missing data for study treatment groups using the distribution implied by the non-missing patient data within the placebo group. The SAS code to impute data for Sensitivity analysis 1 under the MNAR assumption will be of the form:

```
PROC MI DATA=X SEED=<value> NIMPUTE=10 OUT=MI_OUT1 NOPRINT;
CLASS GROUP;
VAR AGE PTA LSurg......;
FCS LOGISTIC(PTS);
RUN;
```

Post imputation each of the imputed 10 datasets will be analyzed using the same approach as for the primary outcome measure. The estimates of the analysis of the 10 imputed datasets will be then combined following Rubin's rules using PROC MIANALYZE procedure in SAS which will be of the form:

```
PROC MIANALYZE PARMS=GMPARMS COVB=GMCOVB PARMINFO=GMPINFO WCOV BCOV

TCOV; / *dataset "gmparms" contains the estimates and associated standard errors
for the mean parameters from each of the M=10 imputed data sets.
dataset "gmcovb" contains the asymptotic covariance matrics
dataset "gmpinfo" contains parameter info*/

MODELEFFECTS INTERCEPT AGE PTA LSurg......;
RUN;
```

Sensitivity 2

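### The sample SAS code for the supportive logistic model and for Sensitivity 2 does not fit the logistic treatment model that the text describes

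*SAP*

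**What the plan says.** **Purpose of the logistic model.** Protocol 12.2.1 (Primary analysis) states it: "To provide an estimate of treatment effect a supportive logistic regression analysis will be done with covariates". The list that follows there and in SAP 7.1.1 is age, pre-op hearing, noise history and noise exposure. Treatment is not in the list.

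**Code for that model (SAP 7.1.1 only).** GROUP is named in the `CLASS` statement. The model line is "MODEL PTS = COVARIATE1 COVARIATE2", and its comment says that the covariates are those already listed. No event level is set.

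**Sensitivity 2 (SAP 7.1.1 and Protocol 12.2.1).** The text describes a tipping-point analysis by logistic regression. The penalty is k × log(OR), where OR is the ZNS-v-placebo odds ratio from what the text calls the primary logistic regression.

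**Step 3 of its code.** The comment reads "Apply the primary MMRM to the 10 complete datasets in Step 2". The call is `PROC GENMOD` with `DESCENDING`. Its model line includes group but has no `DIST=` or `LINK=` option. The output request is "ods output GEEModPEst=gmparms", and there is no `REPEATED` statement. Step 4 then calls `PROC MIANALYZE` with three input data sets (GMPARMS, GMCOVB and GMPINFO). The Protocol carries the same Step 3 and Step 4 code.

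**The concern.** The text and the code specify different analyses, and two planned outputs (SAP Tables 14.2.1.5 and 14.2.1.6) depend on them.

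- Without a treatment term, the logistic model gives no ZNS odds ratio. Its stated purpose fails, and the tipping-point penalty has no input.
- With the normal default, Step 3 fits the treatment effect as a difference in proportions, while the penalty and the text are on the log-odds scale.
- With a GEE table requested but no GEE fitted, Step 3 does not create the table that Step 4 needs.

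Some of these faults would show when the program is run. The missing treatment term and the normal default would not, because both models run without an error. SAP 11.2 validates by having two programmers work independently from the SAP and related specifications. If both copy the same wrong model, their outputs will agree. If one of them departs from the SAP to repair it, the analysis is no longer the pre-specified one.

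**Working it through.** **1. The plan's own figure.** Inputs, all from SAP 2.7: "78 subjects in the ZNS group and 78 subjects in the placebo group"; "we estimate the proportion of PTS positive subjects in the placebo group will be 50"%; "80.4 % power to detect a 50% reduction in the proportion of PTS positive subjects" (50% to 25%); "one-sided alpha level of 0.0125".

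Arcsine approximation with continuity correction for Fisher's test:

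- d = 1/(2 × 78) = 0.00641
- h = asin√(0.5 − d) − asin√(0.25 + d) = 0.7790 − 0.5310 = 0.2480
- power = Φ(h√156 − 2.2414) = Φ(3.098 − 2.241) = 80.4%

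Full enumeration of Fisher's exact test gives 80.7%. The stated power is reproduced and is not in dispute.

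**2. Text against code.**

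| Step | Text requires | Sample code gives |
|---|---|---|
| Supportive model | treatment effect, adjusted | covariates only; GROUP in `CLASS`, not in `MODEL` |
| Penalty | log(OR), ZNS v placebo | no such coefficient |
| Sensitivity 2, Step 3 | logistic model | `GENMOD` with no `DIST=`/`LINK=`, so normal with identity link |
| Output of Step 3 | estimates for pooling | a GEE table, with no `REPEATED` statement |
| Input of Step 4 | estimates from Step 3 | also GMCOVB and GMPINFO, which Step 3 does not create |

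The `GENMOD` default is standard software behaviour and is not stated in the documents. `DESCENDING` does not change the distribution.

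**3. The two models at the planning rates.** Placebo is 50% of 78 = 39. ZNS is 25% of 78 = 19.5, so 19 and 20 bracket it. No covariates and no missing data.

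Logistic, 39/78 v 20/78:

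- log OR = ln[(20/58)/(39/39)] = −1.065
- SE = √(1/39 + 1/39 + 1/20 + 1/58) = 0.344
- z = −3.09

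Normal identity-link, same data:

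- difference = 20/78 − 39/78 = −0.244
- residual variance = (39 × 39/78 + 20 × 58/78)/154 = 0.2232
- SE = √(0.2232 × 2/78) = 0.0756
- z = −3.22

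| ZNS events | Logistic: log OR (SE), z | Normal: difference (SE), z |
|---|---|---|
| 20/78 | −1.065 (0.344), −3.09 | −0.244 (0.076), −3.22 |
| 19/78 | −1.133 (0.348), −3.26 | −0.256 (0.075), −3.41 |

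The normal model's z is larger in size by 0.13 (20 events) and 0.15 (19 events), or 4% to 5%. The SEs use the residual-df scale. `GENMOD`'s maximum-likelihood scale divides by 156 instead of 154, which makes the normal-model SE slightly smaller.

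**4. With covariates.** In 500 simulated trials of 78 per arm, with a log OR of −1.0986 for each ZNS arm, the mean z for one ZNS arm was −3.12 (logistic) and −3.34 (normal). The covariate effects were assumed, since the documents give none: 0.02 per year of age, 0.4 for hearing, 0.3 for noise history and 0.3 per exposure level.

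**5. Event level, if PTS is coded 0/1.** Without `EVENT=` or `DESCENDING`, `PROC LOGISTIC` models the lower value, which is absence of PTS. Once GROUP is added, log(OR) at the planning rates would be −ln[(0.25/0.75)/(0.5/0.5)] = +1.099 instead of −1.099. The `GENMOD` step uses `DESCENDING`, which suggests that presence of PTS was meant.

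**The case against.** The strongest reply is that this is template code and the prose settles the intent. Sensitivity 2 introduces its code as a sample. The code is full of placeholders and cannot run as printed. Both documents say that a logistic model with a treatment effect is meant, GROUP is already in `CLASS`, and a list of covariates often leaves treatment unsaid. Later specifications, parallel programming and review by the lead statistician would probably catch the rest. This stands as mitigation: no competing analysis is specified, and the repair follows from the text. It does not remove the error. The code comment ties the model line to a list without treatment, while the Step 3 model line names group beside its placeholders, so shorthand does not explain the omission.

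The printed code may also be imperfectly reproduced. Underscores seem to be missing, and `RUN` lines present in one document's copy are absent from the other's. That lowers confidence in any point that rests on an absent line. However, `DIST=` and `REPEATED` are absent from both copies.

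A reader might infer three stronger things that the documents do not support:

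- **That an odds ratio near 0.78 would be reported.** exp(−0.244) = 0.78, but only someone who mistook a difference in proportions for a log odds ratio would compute it. No document says to do so.
- **That the trial would pool and report a risk difference.** As printed, Step 3 requests a table that the procedure does not produce, so the run would stop short of pooling. A failed hand-over and a pooled risk difference cannot both describe the same run.
- **That the sign of log(OR) is certainly reversed.** SAP 3.2 codes subjects as PTS-positive or not, without giving values. The reversal depends on 0/1 coding, and it changes neither the size of the effect nor its p-value.

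**Conclusion.** The concern holds as a mismatch between code and specification in the supportive model and in Sensitivity 2. Followed literally, the supportive model gives no treatment estimate, the penalty cannot be computed, and Step 3 fits the wrong model family and passes no estimates to Step 4. The MMRM label refers to nothing in either document.

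The consequence is small. The primary Fisher test, the sample size and the power do not depend on this code. If only the output hand-over were repaired and the normal model kept, the test statistic would move by about 0.13 to 0.15 at the planning rates, and by about 0.22 in the simulation with assumed covariates. How far the tipping point itself would move was not computed. SAP 5.2 expects fewer than 5% drop-outs, which is under 12 of 234 subjects (0.05 × 234 = 11.7), so few values would be imputed.

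The conclusion rests on standard `GENMOD` and `LOGISTIC` defaults and on the code as printed. The event-level part also rests on 0/1 coding of PTS. This is a low-severity correction, worth making before the code is used.

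**What to change.** - **Supportive model (SAP 7.1.1).** Use `CLASS GROUP(REF='Placebo') / PARAM=REF`, with the categorical covariates added to `CLASS`, and `MODEL PTS(EVENT='1') = GROUP` plus the listed covariates. State in SAP 3.2 that 1 denotes PTS-positive.
- **Sensitivity 2, Step 3 (SAP 7.1.1 and Protocol 12.2.1).** Use the same `PROC LOGISTIC`, or keep `GENMOD` with `DIST=BINOMIAL LINK=LOGIT`. Output `ParameterEstimates` in place of the GEE table.
- **Sensitivity 2, Step 4 (both documents).** Make `PROC MIANALYZE` read that table, and drop `COVB=GMCOVB` and `PARMINFO=GMPINFO` or create both data sets in Step 3. Changing the Step 3 output alone leaves Step 4 unable to run.
- **Labels (both documents).** Replace the MMRM reference, and the description of the logistic regression as primary, with: supportive logistic model.

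The cost is a few lines of code and wording in the SAP and the Protocol. No design element, endpoint or primary test changes.
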